5.4 CRITERIA FOR ADJUSTING STUDY DRUG DOSAGE

5.4.1 Dose Delay

Treatment with PCI-32765 should be held for any unmanageable, potentially study drug-related toxicity that is Grade 3 or higher in severity. Subjects who require anticoagulant treatment (e.g., heparin and/or warfarin) should have study drug held until stabilized on anticoagulant therapy.

Study drug may be held for a maximum of 28 consecutive days for toxicity. Study treatment should be discontinued in the event of a toxicity lasting > 28 days, unless reviewed and approved by the medical monitor.

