Study treatment:	PCI-32765 will be administered orally once daily at the same dose level of PCI-32765 as they received in the parent PCI-32765 study. Subject from PCYC-04753 who had disease progression may enroll in this study at a higher dose level of PCI-32765 (not to exceed 840 mg/day) than dose level in PCYC-04753 study. One cycle is 28 days.		
Concomitant therapy and clinical practice:	Concomitant medications which are permitted while on study treatment are provided in Section 5.5.1.		
	Any chemotherapy (e.g., chlorambucil, bendamustine, cyclophosphamide, pentostatin, or fludarabine), anticancer immunotherapy (e.g., rituximab, alemtuzumab, or ofatumumab), experimental therapy, or radiotherapy are prohibited during the Treatment Phase. Localized, hormonal, or bone sparing treatment for non-B-cell malignancies may be considered with approval of the medical monitor. Localized radiotherapy for medical conditions other than the underlying B-cell malignancies are allowed after consultation and approval by the medical monitor. Corticosteroids at dosages equivalent to prednisone >20mg/day administered consecutively for 14 days or longer are prohibited. For medications to be used with caution refer to Section 5.6.		
Statistical methods:	No formal statistical tests of hypotheses will be performed as this is an open-label, long-term, follow-up study. This study will remain open as long as there are active studies of PCI-32765 with subjects who could be eligible for this protocol.		
	Demographic characteristics, laboratory parameters, concomitant therapy, and AE incidence rates will be summarized using descriptive statistics. All subjects who receive at least 1 dose of study drug will be included in the safety and efficacy analyses.		
	All available efficacy and safety data will be included in data listings and tabulations. No imputation of values for missing data will be performed. Subjects lost to follow-up will be included in statistical analyses to the point of their last evaluation. All study data will be examined using standard data management operating procedures.		

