5.4.2 Dose Reduction and Discontinuation

At the discretion of the investigator, based upon the recent FDA approvals of IMBRUVICA® (PCI-32765) for the treatment of MCL and CLL after having received at least one prior therapy and for the treatment of WM, subjects may have their PCI-32765 dose reduced to the approved dosage in the absence of toxicity. Any subsequent dose modifications below the approved label dose should follow the dose modification guidelines per protocol for toxicity.

The actions in Table 1 should be taken for the following toxicities:

• Grade 4 ANC ($< 500/\mu$ L) for > 7 days (neutrophil growth factors are permitted per ASCO guidelines ¹⁶ and use must be recorded in CRF).

- Grade 3 thrombocytopenia ($< 50,000/\mu L$) in the presence of clinically significant bleeding events.
- Grade 4 thrombocytopenia (< 25,000/μL).
- Grade 3 or 4 nausea, vomiting, or diarrhea, if persistent despite optimal antiemetic and/or anti-diarrheal therapy.
- Any other Grade 4 toxicity or any unmanageable Grade 3 toxicity.

For Grade 3 or 4 atrial fibrillation or persistent atrial fibrillation of any grade, consider the risks and benefits of PCI-32765 treatment. If clinically indicated, the use of anticoagulants or antiplatelet agents may be considered for the thromboprophylaxis of atrial fibrillation (Section 5.6.4).

Table 1: Drug Discontinuation Actions for Subjects on PCI-32765

Occurrence	Action
1 st	Hold PCI-32765 until recovery to Grade ≤ 1 or baseline; may restart at original dose level
2 nd Hold PCI-32765 until recovery to Grade ≤ 1 or baseline; restart at one dose level lower (140mg less daily)*	
3 rd	Hold PCI-32765 until recovery to Grade ≤ 1 or baseline; restart at one dose level lower (140mg less daily)*
4 th	Discontinue PCI-32765

^{*} Reference Table 2 for details on dose de-escalation of 420, 560 and 840 mg dose group.

Changes must be recorded in the Dose Administration eCRF and subject's records.

A high number of circulating malignant cells (>400000/mcL) may confer increased risk of leukostasis; these subjects should be closely monitored. Administer supportive care such as hydration and/or leukophoresis as indicated. PCI-32765 may be temporarily held, and medical monitor should be contacted.

Table 2: Intrasubject Dose De-escalation

Assigned Daily Dose	420 mg	560 mg	840 mg
	(3 x 140-mg)	(4 x 140-mg)	(6 x 140-mg)
Dose De-escalation Level 1	280 mg	420 mg	700 mg
	(2 x 140-mg)	(3 x 140-mg)	(5 x 140-mg)

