5.6.4 Concomitant Use of Antiplatelet Agents and Anticoagulants

Warfarin or vitamin K antagonists should not be administered concomitantly with PCI-32765. Supplements such as fish oil and vitamin E preparations should be avoided. Use PCI-32765 with caution in subjects requiring other anticoagulants or medications that inhibit platelet function. Subjects with congenital bleeding diathesis have not been studied. For guidance on PCI-32765 and the use of anticoagulants during procedures/surgeries see Section 5.6.5.

Subjects requiring the initiation of therapeutic anticoagulation therapy (e.g., atrial fibrillation), consider the risks and benefits of continuing PCI-32765 treatment. If therapeutic anticoagulation is clinically indicated, treatment with PCI-32765 should be held and not be restarted until the subject is clinically stable and has no signs of bleeding. No dose reduction is required when study drug is restarted.

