6.1 DESCRIPTION OF PROCEDURES

Informed Consent

Screening

The subject must read, understand and sign the IRB-approved informed consent form (ICF) confirming his or her willingness to participate in this study before initiating any screening activity that is not standard of care. Subjects must also grant permission to use protected health information.

Medical History

Screening

Medical history, concomitant medications, and any ongoing signs or symptoms from the prior PCI-32765 protocol must be recorded in the site's source documentation.

Adverse Events

At all visits (except Post-treatment and Post-PD follow up assessments)

The accepted regulatory definition for an AE is provided in Section 7.1. Adverse events that meet the criteria for SAEs, events of special interest (Section 7.2.4), and AEs of grade 3 or higher in severity will be recorded from the subject's first dose of study drug until 30 days after study drug discontinuation or start of a new anticancer therapy. Important additional requirements for reporting SAEs are explained in Section 7.2.

Concomitant Medication Use

At screening visit and during study when associated with protocol specified AE or SAE. Verify concomitant medication use to ensure subjects' eligibility to remain on study and when associated with a protocol specified AE/SAE. See Section 7.0 for further AE/SAE details.

Confirmation of Eligibility

Screening

Perform all necessary procedures and evaluations to document that the subject meets each eligibility criterion. Screening evaluations must be completed within 14 days before the subject's first dose of PCI-32765 under this protocol.

Physical Examination and Vital Signs

At all visits (except Post treatment and Post PD follow up assessments)

The screening physical examination will include, at a minimum, the general appearance of the subject, height (screening only) and weight, and examination of the skin, eyes, ears, nose, throat, lungs, heart, abdomen, extremities, musculoskeletal system, nervous system, and lymphatic system.

Symptom-directed physical exams will be done during the treatment period and at the Safety Follow-up Visit.

Vital signs will include blood pressure, pulse, respiratory rate, and body temperature. Vital signs and weight will be measured at every visit. Screening vital signs and weight do not need to be repeated if performed on prior PCI-32765 protocol within 14 days before the first administration of study drug on this protocol.

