Appendix 3. Schedule of Assessments

	Screeninga	Treatment Phase	Follow-up Phase		
		Safety and Efficacy Every 3 Cycles (84 days) ±7 days	Safety Follow-up Prior to anticancer tx or 30 (±7) days after last dose	Post-treatment Follow-up every 3 cycles (84 days) ±7 days until PD ^b	Post-PD Follow-up every 3 months (±7 days)
Informed consent	X				
Confirm eligibility	X				
Medical history	X				
PE ^c /Vital signs ^d /Weight ^d	X	X	X		
Eye-related symptoms	X	X	X		
ECOG status		X	X		
Lab assessments:					
Urine pregnancy test ^e	X		X		
Hematology ^t	X	X	X		
Serum chemistry ^g	X	X	X		
Pharmacodynamics & Pharmacokinetics ¹		Will only be collected when a subject progresses			
Predictive biomarkers & mechanisms of resistance		Approximately once per year			
ECG		If clinically ir	dicated (eg, subjects with palpitations,	lightheadedness)	
Dispense study drug ^h		X			
Study drug compliance		X			
Disease assessment ¹		X		X	
Concomitant medications ^j	X	X	X		
New anti-cancer treatment ^m	•		X	X	X
Adverse events ^k	X	X	X		
Survival			_		X

- a. Screening tests should be performed within 14 days before the first administration of study drug, unless otherwise indicated.
- b. Subjects who did not progress on treatment, but discontinued study drug will be followed every 3 cycles for disease progression.
- c. The screening PE will include, at a minimum, the general appearance of the subject, height (screening only) and weight, and examination of the skin, eyes, ears, nose, throat, lungs, heart, abdomen, extremities, musculoskeletal system, nervous system, and lymphatic system. Symptom-directed physical examinations will be performed thereafter.
- d. Vital signs (blood pressure, pulse, respiratory rate, and temperature) will be assessed. Screening vital signs and weight do not need to be repeated if performed during a prior PCI-32765 protocol within 14 days before the first administration of study drug during the current protocol.
- e. Women of childbearing potential only. If positive, pregnancy must be ruled out by ultrasound to be eligible.

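### Section 5.4.1 implies that study drug may resume in a subject stabilised on warfarin; Section 5.6.4 says the two drugs should not be combined

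*Protocol*

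**What the plan says.** Two sections of the protocol tell the site what to do when a subject needs an anticoagulant.

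- **Section 5.4.1 (Dose Delay):** "Subjects who require anticoagulant treatment (e.g., heparin and/or warfarin) should have study drug held until stabilized on anticoagulant therapy".
- **Section 5.6.4 (antiplatelet agents and anticoagulants):** "Warfarin or vitamin K antagonists should not be administered concomitantly with PCI-32765". It then deals with everything else: "Use PCI-32765 with caution in subjects requiring other anticoagulants or medications that inhibit platelet function". When therapeutic anticoagulation is started, study drug "should be held and not be restarted until the subject is clinically stable and has no signs of bleeding".

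Three other places touch the subject. Section 5.4.2 allows anticoagulants to be considered for atrial fibrillation and points to Section 5.6.4. The synopsis says: "For medications to be used with caution refer to Section 5.6". Section 6.1 requires a check of concomitant medication ("Verify concomitant medication use to ensure" that the subject may remain on study). Appendix 3 places that check at screening, at the treatment visits ("Safety and Efficacy Every 3 Cycles (84 days) ±7 days") and at the safety follow-up visit.

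**The concern.** A hold that lasts until the subject is stable on an anticoagulant ends while the anticoagulant is still being taken. Because Section 5.4.1 gives warfarin as an example, a site that follows it would restart PCI-32765 in a subject on warfarin. That is the combination Section 5.6.4 says should not be given.

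What is at stake is subject safety. Section 1.4.3.2 reports major and fatal bleeding on study drug, and Section 7.2.4.1 makes major hemorrhage an event of special interest, reportable within 24 hours under Section 7.2.4. Of the two instructions, the one in 5.4.1 is the less cautious.

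**Working it through.** No rate, error probability or sample size is involved, so the check is a comparison of the two rules and a search for text that reconciles them.

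**1. The rules side by side**

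| Point | Section 5.4.1 | Section 5.6.4 |
|---|---|---|
| Warfarin | Named example of an anticoagulant to which the hold applies | Not to be given with study drug; no exception stated |
| Heparin and other anticoagulants | Heparin is a named example | Allowed, with caution |
| What ends the hold | Stabilised on the anticoagulant (1 condition) | Clinically stable; no signs of bleeding (2 conditions) |
| Link to the other section | None | None to 5.4.1 |

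**2. Apply both rules to a subject**

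- *On heparin:* hold, then restart once anticoagulation is stable (5.4.1) and the subject is clinically stable without bleeding (5.6.4). All 1 + 2 = 3 conditions can be met together, so there is no conflict.
- *On warfarin:* under 5.4.1 the hold ends once the subject is stable on warfarin. Under 5.6.4 the drugs should not be taken together, however stable the subject is. The two sections give different answers.

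**3. Look for text that settles it**

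- Warfarin is named in 2 sections, 5.4.1 and 5.6.4, and they differ.
- Section 5.6.4 is cited by number from 1 other section (5.4.2) and 0 times from 5.4.1.
- Section 5.6 as a whole is cited once, in the synopsis, and only for drugs to be used with caution. That does not tell the reader that one of them is barred.
- The prohibited therapies in Section 5.5.2 and the exclusion criteria in Section 4.2 do not name warfarin.
- The medication check in Section 6.1 does not name it either. During treatment its scheduled interval is 3 cycles × 28 days = 84 days (±7). The Appendix 3 footnote asks for on-study medications to be recorded only when associated with a protocol-specified AE or an SAE, so warfarin use without such an event need not reach the database.

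None of these passages reconciles the two rules or gives one precedence.

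**The case against.** The strongest reply is that 5.4.1 only tells the site to hold study drug and lists anticoagulants by way of illustration. It nowhere says in terms that study drug may be restarted on warfarin. Section 5.6.4 is the dedicated section and its rule is categorical, so a site that reads both can comply: hold under 5.4.1, and do not resume while warfarin continues under 5.6.4. Restart on warfarin is indeed implied and not stated. But on this reading stabilisation could never end the hold for a subject on warfarin, so the end-point that 5.4.1 sets would have no function for one of its two named examples. Both rules are also worded as recommendations of equal force.

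Three further points stand in part:

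- A reader dealing with atrial fibrillation is sent by 5.4.2 to 5.6.4 and will find the bar there. Other indications are not routed that way.
- The screening check of concomitant medication gives a chance to notice a subject who rolls over already on warfarin. It does not tell the site what to do about it.
- No consequence is quantified. Section 1.4.3.2 does not discuss anticoagulant co-use, so the judgement that 5.4.1 is less safe rests on the protocol's own bar in 5.6.4.

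It can also be argued that the fix should stop at deleting warfarin and adding the cross-reference, because 5.6.4 ties its restart conditions to the start of therapeutic anticoagulation. Anticoagulant treatment in 5.4.1 is in substance the same thing, so carrying those conditions over does no harm.

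**Conclusion.** The concern holds. On warfarin, Section 5.4.1 as written leads to a combination that Section 5.6.4 says should not be given, and no other text resolves it. The conclusion rests on reading the end of the 5.4.1 hold as permission to restart, which is the only reading that gives it a function for warfarin.

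The defect is narrow: one sentence, and only warfarin and other vitamin K antagonists. The number of subjects affected is unknown, because the protocol gives neither the frequency of such use nor the added bleeding risk. The primary endpoint and the planned descriptive analyses are not in question. It should be fixed because it is a safety instruction for a drug with reported fatal bleeding.

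**What to change.** Replace the anticoagulant sentence in Section 5.4.1 with wording such as:

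> *For subjects who need an anticoagulant (for example heparin), hold PCI-32765 until anticoagulation is stable, the subject's clinical condition is stable and there is no sign of bleeding. Do not combine warfarin or any other vitamin K antagonist with PCI-32765 (see Section 5.6.4).*

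This removes warfarin as an example, keeps the existing stabilisation condition, adds the two conditions from 5.6.4 so that all three appear in one place, and supplies the missing cross-reference. It introduces no new clinical policy, since each element is already in 5.4.1 or 5.6.4. The cost is a one-sentence change in the next amendment and a notification to sites.

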5.4.2 Dose Reduction and Discontinuation

At the discretion of the investigator, based upon the recent FDA approvals of IMBRUVICA® (PCI-32765) for the treatment of MCL and CLL after having received at least one prior therapy and for the treatment of WM, subjects may have their PCI-32765 dose reduced to the approved dosage in the absence of toxicity. Any subsequent dose modifications below the approved label dose should follow the dose modification guidelines per protocol for toxicity.

The actions in Table 1 should be taken for the following toxicities:

• Grade 4 ANC ($< 500/\mu$ L) for > 7 days (neutrophil growth factors are permitted per ASCO guidelines ¹⁶ and use must be recorded in CRF).

- Grade 3 thrombocytopenia ($< 50,000/\mu L$) in the presence of clinically significant bleeding events.
- Grade 4 thrombocytopenia (< 25,000/μL).
- Grade 3 or 4 nausea, vomiting, or diarrhea, if persistent despite optimal antiemetic and/or anti-diarrheal therapy.
- Any other Grade 4 toxicity or any unmanageable Grade 3 toxicity.

For Grade 3 or 4 atrial fibrillation or persistent atrial fibrillation of any grade, consider the risks and benefits of PCI-32765 treatment. If clinically indicated, the use of anticoagulants or antiplatelet agents may be considered for the thromboprophylaxis of atrial fibrillation (Section 5.6.4).

Table 1: Drug Discontinuation Actions for Subjects on PCI-32765

Occurrence	Action
1 st	Hold PCI-32765 until recovery to Grade ≤ 1 or baseline; may restart at original dose level
2 nd Hold PCI-32765 until recovery to Grade ≤ 1 or baseline; restart at one dose level lower (140mg less daily)*	
3 rd	Hold PCI-32765 until recovery to Grade ≤ 1 or baseline; restart at one dose level lower (140mg less daily)*
4 th	Discontinue PCI-32765

^{*} Reference Table 2 for details on dose de-escalation of 420, 560 and 840 mg dose group.

Changes must be recorded in the Dose Administration eCRF and subject's records.

A high number of circulating malignant cells (>400000/mcL) may confer increased risk of leukostasis; these subjects should be closely monitored. Administer supportive care such as hydration and/or leukophoresis as indicated. PCI-32765 may be temporarily held, and medical monitor should be contacted.

Table 2: Intrasubject Dose De-escalation

Assigned Daily Dose	420 mg	560 mg	840 mg
	(3 x 140-mg)	(4 x 140-mg)	(6 x 140-mg)
Dose De-escalation Level 1	280 mg	420 mg	700 mg
	(2 x 140-mg)	(3 x 140-mg)	(5 x 140-mg)
Dose De-escalation Level 2	140 mg	280 mg	560 mg
	(1 x 140-mg)	(2 x 140-mg)	(4 x 140-mg)

5.4.3 Intrasubject Escalation

At the Investigator's discretion, the dose of study drug may be re-escalated after 2 cycles following a dose reduction in the absence of a recurrence of the toxicity that led to the reduction. Dose changes must be recorded in the Dose Administration eCRF.

5.4.4 Dose Modification for Hepatic Impaired Subjects

PCI-32765 is metabolized in the liver. For subjects who develop mild liver impairment while on study (Child-Pugh class A), the recommended dose reduction for PCI-32765 is to a level of 280 mg daily (two capsules). For subjects who develop moderate liver impairment while on study (Child-Pugh class B), the recommended dose reduction is to a level of 140 mg daily (one capsule). Subjects who develop severe hepatic impairment (Child-Pugh class C) must hold study drug until resolved to moderate impairment (Child-Pugh class B) or better and could be re-treated according to resolved hepatic conditions (ie, 140 mg or 280 mg for moderate or mild impairment, respectively). Monitor subjects for signs of toxicity and follow dose modification guidance as needed Appendix 7.

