1.3.3 Pharmacokinetics and Product Metabolism

Following oral administration of PCI-32765 at doses ranging from 1.25 to 12.5 mg/kg/day as well as fixed dose levels of 420, 560, and 840 mg/day, exposure to PCI-32765 increased as doses increased with substantial intersubject variability. The mean half life ($t_{1/2}$) of PCI-32765 across 3 clinical studies ranged from 4 to 9 hours, with a median time to maximum plasma concentration (T_{max}) of 2 hours. Administration of 420 mg PCI-32765 with a high-fat breakfast in subjects with chronic lymphocytic leukemia (CLL) approximately doubled the mean systemic exposure compared to intake after overnight fasting with median time to T_{max} delayed from 2 to 4 hours. PCI-32765 was extensively metabolized to the dihydrodiol metabolite PCI-45227, a reversible inhibitor of Btk, with approximately 15 times lower inhibitory potency compared to PCI-32765. The metabolite-to-parent AUC ratio ranged from 0.7 to 3.4. Steady-state exposure of PCI-32765 and PCI-45227 was less than 2-fold of first dose exposure.

The results of human mass balance study of [\frac{14}{C}]-PCI-32765 conducted in six healthy male subjects demonstrated that less than 10% of the total dose of [\frac{14}{C}]-PCI-32765 is renally excreted, whereas approximately 80% is recovered in feces. Subjects with mild and moderate renal insufficiency (creatinine clearance >30 mL/min) were eligible to enroll in Study PCYC-1102-CA in which pharmacokinetic (PK) assessments were included. No dose adjustment is needed for mild or moderate renal impairment (greater than 30 mL/min creatinine clearance). There is no data in patients with severe renal impairment or patients on dialysis. In a hepatic impairment study, data showed an increase in PCI-3276 exposure. Following single dose administration, the AUC of PCI-32765 increased 2.7-, 8.2-, and 9.8-fold in subjects with mild (Child-Pugh class A), moderate (Child-Pugh class B), and severe (Child-Pugh class C) hepatic impairment compared to subjects with normal liver function. The safety of PCI-32765 has not been evaluated in patients with hepatic impairment.

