5.6 MEDICATIONS TO BE USED WITH CAUTION

5.6.1 CYP3A Inhibiting/Inducing Agents

PCI-32765 is metabolized primarily by CYP3A. Avoid co-administration with strong or moderate CYP3A inhibitors and consider alternative agents with less CYP3A inhibition. Coadministration of ketoconazole, a strong CYP3A inhibitor, in 18 healthy subjects increased dose normalized exposure, C_{max} and AUC_{0-last}, of PCI-32765 by 29- and 24-fold, respectively. The maximal observed PCI-32765 exposure (AUC) was ≤2-fold in 37 patients treated with mild and/or moderate CYP3A inhibitors when compared with the highest PCI-32765 exposure in 76 patients not treated concomitantly with CYP3A inhibitors. Clinical safety data in 66 patients treated with moderate (n=47) or strong CYP3A inhibitors (n=19) did not reveal meaningful increases in toxicities. Strong inhibitors of CYP3A (e.g., ketoconazole, indinavir, nelfinavir, ritonavir, saquinavir, clarithromycin, telithromycin, itraconazole, and nefazadone) should be avoided. If a strong CYP3A inhibitor must be used, reduce the PCI-32765 dose to 140 mg or withhold treatment temporarily. Subjects should be monitored for signs of PCI-32765 toxicity. If a moderate CYP3A inhibitor must be used, reduce PCI-32765 to 140 mg for the duration of the inhibitor use. No dose adjustment is required in combination with mild inhibitors. Avoid grapefruit and Seville oranges during PCI-32765 treatment, as these contain moderate inhibitors of CYP3A (see Section 5.3).

Co-administration of PCI-32765 with a strong CYP3A inducer, rifampin, in healthy subjects decreases PCI-32765 plasma concentrations by approximately 10-fold. Avoid concomitant use of strong CYP3A inducers (e.g., carbamazepine, rifampin, phenytoin, and St. John's Wort). Consider alternative agents with less CYP3A induction.

A list of common CYP3A inhibitors and inducers is provided in Appendix 2; a comprehensive list of inhibitors, inducers, and substrates may be found at http://medicine.iupui.edu/clinpharm/ddis/table.aspx. This website is continually revised and should be checked frequently for updates.

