- f. Hematology includes complete blood count with differential and platelet count. Screening hematology does not need to be repeated if performed on prior PCI-32765 protocol within 14 days before the first administration of study drug on this protocol. Subjects who roll into PCYC-1103-CA Study with < 12 months of study drug exposure will need to have hematology performed every 30 days (±7 days) till completion of 12 months on study drug and then hematology will be extended to every 3 cycles (±7 days) while on study treatment.
- g. Serum chemistry includes glucose, calcium, albumin, total protein, sodium, potassium, CO₂, chloride, blood urea nitrogen (BUN), creatinine, alkaline phosphatase, ALT, AST, and total bilirubin. Screening chemistry does not need to be repeated if performed on prior PCI-32765 protocol within 14 days before the first administration of study drug on this protocol. Serum chemistry will be performed every 3 cycles while on study treatment.
- h. One cycle is once daily administration for 28 days. Dispense sufficient study drug until the next scheduled visit.
- i. Objective response will be categorized as complete response (CR), partial response (PR), stable disease, or progressive disease based on the guidelines of each histology (refer to Appendix 4, Appendix 5 and Appendix 6. The response assessments will be performed once every 3 cycles during the Treatment Phase. All responses must be maintained for at least 2 months to be considered confirmed. Complete responses (CRs) must be confirmed by bone marrow biopsy/aspirate. Progressive disease (PD) must be confirmed by CT. To facilitate lymph node, liver, and spleen assessments in subjects, obtain a CT scan of the chest, abdomen, and pelvis, every 3 cycles for the first 18 cycles from the subject's first dose of study drug in the parent study, then every 6 cycles up to cycle 36, then every 12 cycles (annually) thereafter.
- 1. Verify concomitant medication use to ensure subjects' eligibility to remain on study. Record concomitant medications at screening visit and when associated with protocol specified AEs and with SAEs.
- k. Grade 3 and 4 AEs as well as all SAEs, exceptions (refer to Section 7.1.1) and events of special interest to be collected (refer to Section 7.2.4
- 1. Pharmacodynamic and Pharmacokinetic samples to be collected at the visit when it is determined that the subject has PD.

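### On the protocol's own AUC ratios, the hepatic-impairment doses in section 5.4.4 leave subjects assigned 420 or 560 mg above their assigned exposure

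*Protocol*

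**What the plan says.** Section 5.4.4 sets one dose per Child-Pugh class, whatever dose the subject was assigned. For mild impairment (class A), "the recommended dose reduction for PCI-32765 is to a level of 280 mg daily (two capsules". For moderate impairment (class B), "the recommended dose reduction is to a level of 140 mg daily (one capsule". Only class C carries a mandatory hold: such subjects "must hold study drug until resolved to moderate impairment (Child-Pugh class B) or better and could be re-treated according to resolved hepatic conditions", meaning 140 mg once back in class B and 280 mg once in class A. The section also asks for monitoring for toxicity, without an interval.

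The pharmacokinetic basis is in section 1.3.3. After a single dose, "the AUC of PCI-32765 increased 2.7-, 8.2-, and 9.8-fold in subjects with mild (Child-Pugh class A), moderate (Child-Pugh class B"; the third figure, 9.8, is for class C. The same section states: "The safety of PCI-32765 has not been evaluated in patients with hepatic impairment".

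Table 2 lists assigned doses of 420, 560 and 840 mg. Sections 5.2 and 5.3 make an intact 140 mg capsule the smallest unit. On scheduled laboratory checks, Appendix 3 says: "Serum chemistry will be performed every 3 cycles while on study treatment". Three cycles are 84 days. Section 6.0 permits more frequent tests where clinically indicated but does not require them.

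**The concern.** A dose reduction for impaired clearance would normally aim to bring exposure back near the level the subject was tolerating. Set against the 1.3.3 ratios, the 5.4.4 doses appear to fall short of that for two of the three assigned doses, and most clearly in class B. A subject could have the dose cut from 420 to 140 mg and still have more than twice the previous exposure.

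What is at stake is subject safety, in a group for which the protocol says it has no safety evaluation. Section 1.4.3.2 records major bleeding, including fatal events, on this drug. Appendix 7 makes PT INR part of the Child-Pugh score, so class B can include subjects with impaired coagulation. Following the recommendation puts these subjects on drug by default, and the only fixed laboratory schedule is every 84 days.

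**Working it through.** The protocol states no exposure figure for 5.4.4, so there is nothing of its own to reproduce.

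**Inputs.** AUC ratios k = 2.7 (class A) and 8.2 (class B), single dose, from section 1.3.3. Recommended doses of 280 mg (A) and 140 mg (B) from 5.4.4. Assigned doses of 420, 560 and 840 mg from Table 2.

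**Assumptions.** Exposure is proportional to dose (1.3.3 says only that it rises with dose, with substantial variability), and the single-dose ratio carries over to daily dosing.

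**Formula.** Normal-liver mg-equivalent = recommended dose × k. Relative exposure = mg-equivalent / assigned dose.

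- Class B at 140 mg: 140 × 8.2 = 1148 mg-equivalent.
- Class A at 280 mg: 280 × 2.7 = 756 mg-equivalent.

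| Assigned dose | Class B, 140 mg | Class A, 280 mg |
|---|---|---|
| 420 mg | 1148/420 = 2.73 | 756/420 = 1.80 |
| 560 mg | 1148/560 = 2.05 | 756/560 = 1.35 |
| 840 mg | 1148/840 = 1.37 | 756/840 = 0.90 |

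**Sensitivity to proportionality.** Let AUC rise as dose^b. Relative exposure is then k × (recommended/assigned)^b, and the excess vanishes at b = ln k / ln(assigned/recommended).

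| Case | b = 0.8 | b = 1.2 | Break-even b |
|---|---|---|---|
| Class B, 420 mg | 3.40 | 2.19 | ln 8.2/ln 3 = 1.92 |
| Class B, 560 mg | 2.70 | 1.55 | ln 8.2/ln 4 = 1.52 |
| Class B, 840 mg | 1.96 | 0.96 | ln 8.2/ln 6 = 1.17 |
| Class A, 420 mg | 1.95 | 1.66 | ln 2.7/ln 1.5 = 2.45 |
| Class A, 560 mg | 1.55 | 1.18 | ln 2.7/ln 2 = 1.43 |

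The excess is secure for 420 and 560 mg in class B and for 420 mg in class A. For 560 mg in class A the margin is thinner. For 840 mg it is not robust.

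**Sensitivity to the ratio.** No interval is given for k. At proportional exposure, 140 mg in class B would match the assigned exposure only if k were 3.0 (420 mg), 4.0 (560 mg) or 6.0 (840 mg), against a stated 8.2. For 280 mg in class A the matching values are 1.5, 2.0 and 3.0, against 2.7.

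**Doses that would match.** Class B: 420/8.2 = 51 mg, 560/8.2 = 68 mg and 840/8.2 = 102 mg, all below one capsule. At daily dosing, a hold is therefore the only lower option. Class A: 420/2.7 = 156 mg, 560/2.7 = 207 mg and 840/2.7 = 311 mg.

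**Class A at 140 mg.** 140 × 2.7 = 378 mg-equivalent: 0.90 of 420 mg (1.12 to 0.72 for b from 0.8 to 1.2), 0.68 of 560 mg and 0.45 of 840 mg. Section 1.1 reports maximal pharmacodynamic activity from 2.5 mg/kg; 378/2.5 = 151 kg, so the 378 mg-equivalent reaches that level for body weights up to 151 kg.

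**The case against.** The strongest reply is that matching the assigned exposure is the reviewer's yardstick. Section 5.4.4 does not claim to do it, and the protocol refers to the Investigator's Brochure for fuller data. Exposure near 1148 mg-equivalent is also not plainly outside what the protocol accepts. Section 1.3.3 says a high-fat breakfast about doubled exposure at 420 mg, and 5.3 sets no fasting rule, so 560 mg with such a meal could be about 1120 mg-equivalent. Doses up to 12.5 mg/kg/day were given, which is about 1150 mg at an assumed 92 kg. Section 5.6.1 reports no meaningful increase in toxicity in 66 patients on moderate or strong CYP3A inhibitors. The 5.4.4 doses are recommendations, so an investigator may already hold, and 5.4.1 and Table 1 govern holds and reductions for toxicity. All of this stands. It makes harm uncertain and limits the size of the change that is justified, but it does not supply safety data in hepatic impairment.

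Four stronger readings are tempting, and the documents do not support them.

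- **That 5.4.4 contradicts 5.6.1.** For moderate CYP3A inhibitors, 5.6.1 says: "If a moderate CYP3A inhibitor must be used, reduce PCI-32765 to 140 mg for the duration of the inhibitor use". That looks stricter than 280 mg at 2.7-fold. However, the 2-fold figure there compares maximal exposures and pools mild and moderate inhibitors. For strong inhibitors the instruction is to "reduce the PCI-32765 dose to 140 mg or withhold treatment temporarily", although ketoconazole raised AUC 24-fold (140 × 24 = 3360 mg-equivalent). The comparison cuts both ways.
- **That holding at 9.8-fold but dosing at 8.2-fold is illogical.** The AUC ratio falls only 16% from C to B (1 − 8.2/9.8) and 67% from B to A (1 − 2.7/8.2). However, 5.4.4 does not say that the class C hold rests on AUC alone, and class C is a much sicker state.
- **That every class A subject should drop to 140 mg.** This fails for 840 mg, at 0.45 of assigned exposure.
- **That 840 mg/day is an exposure limit that class B breaches.** It is a dose cap, and the meal effect alone can exceed its fasted equivalent.

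**Conclusion.** The point holds in limited form. On the 1.3.3 ratios, the recommended reductions leave exposure at about 2.7 times (420 mg) and 2.1 times (560 mg) the assigned level in class B, and at about 1.8 and 1.35 times in class A, in patients whose safety on the drug is unevaluated. No robust excess is shown for 840 mg. The result rests on rough dose proportionality and on single-dose ratios, given without an interval, carrying over to daily dosing.

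A reader might infer that class B must be a hold without exception. The documents do not settle that: these subjects have recurrent disease, 140 mg is the smallest dose, and stopping has its own cost. A reader might also infer that the trial's results would be biased. Section 8.0 plans descriptive summaries and listings only, with no adverse-event analysis by dose, so no planned analysis is shown to be distorted. The number affected is not given and is probably small. The change is worth making because it is cheap and protects subjects, with medium confidence.

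**What to change.** Amend section 5.4.4 as follows.

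1. **Class A.** Define it as newly developed hepatic impairment scoring 5 to 6. A score of 5 is the minimum in Appendix 7 and should not trigger a reduction by itself. Give 140 mg daily to subjects assigned 420 mg (0.90 of assigned exposure; 140 mg is already a Table 2 level). Keep 280 mg for subjects assigned 840 mg (0.90). For 560 mg, allow 140 or 280 mg at the investigator's discretion (0.68 or 1.35).
2. **Class B, including restart after class C.** Allow 140 mg daily only after the medical monitor has reviewed and approved the benefit-risk, with serum chemistry and toxicity checks at least every 28 days while class B persists. Otherwise hold until class A. Section 5.4.1 already uses medical monitor review for long holds, so no new body is needed.

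Two details need a line in the amendment. It should say which rule applies to subjects on other doses, such as the reduced levels in Table 2. Re-scoring the class also needs PT INR, which is not in the hematology and chemistry panels listed in section 6.1.

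The cost is protocol wording, a short interruption while approval is sought, and some extra laboratory tests for a few subjects. The real downside is possible loss of treatment for class B subjects who are not approved. Subjects assigned 560 mg who are put on 140 mg in class A would run at about two thirds of assigned exposure.
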